#### 5.1.8. Early Termination Visit

In the event of termination prior to Visit 6, every attempt will be made to ensure that all Visit 6 assessments are performed. If this is not feasible, at least the following should be performed/assessed:

- Use of any concomitant medications since the last visit
- Occurrence of any AEs since the last visit
- Used and unused investigational product collected and compliance [REDACTED]

- [REDACTED]
- BCVA
- Slit lamp biomicroscopy
- IOP measurement

## 5.2. RESCUE MEDICATION USE

Any subjects not responding adequately to the study medication may be rescued and placed on alternate therapy at the Investigator's discretion at any time. The choice of rescue medication is at the Investigator's discretion. Any subject placed on rescue therapy will discontinue use of the study medication and continue study participation through Visit 6. Rescued subjects will be considered treatment failures, but the need for rescue therapy will not be considered an AE. Rescued subjects experiencing an AE at the time of rescue will be followed through stabilization or resolution of the AE or the end of the study (whichever comes last). Rescued subjects should not be withdrawn from the study, but rather followed to resolution of signs and symptoms or until the Investigator has deemed the subject is stable.

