## 5.3. SUBJECT WITHDRAWAL AND/OR DISCONTINUATION

Any subject who wishes to may withdraw from the investigational product use or from participation in the study of his or her own accord for any reason is entitled to do so without obligation. The Investigator may also withdraw any subject from the investigational product use or from study participation, if deemed necessary.

Investigational product use may be discontinued and any subject may be discontinued from study participation at any time during the study at the discretion of the Investigator or the sponsor for any reason including but not limited to:

1. Occurrence of any medical condition or circumstance that exposes the subject to substantial risk and/or does not allow the subject to adhere to the requirements of the protocol.
2. Any SAE, clinically significant AE, severe laboratory abnormality, intercurrent illness, or other medical condition that indicates to the Investigator that continued participation is not in the best interest of the subject.
3. Subject's decision to withdraw.
4. Any woman who becomes pregnant while participating in the study. Information on the pregnancy and outcome will be requested.
5. Subject's failure to comply with protocol requirements or study related procedures.
6. Termination of the study by the Sponsor, FDA, or other regulatory authorities.

In the event study discontinuation of a randomized subject is necessary, the Investigator should make every attempt to have subject complete Visit 6 assessments as possible. If a non-serious AE is unresolved at the time of the subject's final study visit, an effort will be made to follow up until the AE is resolved or stabilized, the subject is lost to follow-up, or there is some other resolution of the event. The Investigator should make every attempt to follow all serious adverse events (SAEs) to resolution. The reason for premature discontinuation should be entered onto the Case Report Form (CRF) and recorded in the subject chart.

Subjects who withdraw from the study will not be replaced.

Additionally, the trial or parts of the trial may be discontinued by the sponsor or at the recommendation of the Investigator after consultation with Kala Pharmaceuticals, Inc. This may be based on a significant number of AEs of a similar nature that warrant such action.

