#### 6.2.1. Permitted Medications

Medications not specifically excluded in [Section 6.2.2](#) may be taken as necessary.

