#### 6.2.2. Medications Not Permitted

At **Visit 1 (Screening)** and for the duration of the study:

- Any topical ophthalmic medications including eyelash growth medications, eye drops, gels, or artificial tears
- TNF-blocking agents (e.g. etanercept, adalimumab, infliximab)
- Treatment for glaucoma

Within **30 days** prior to screening (Visit 1) and for the duration of the study:

- Ocular, inhaled, or intranasal corticosteroids
- Ocular or oral non-steroidal anti-inflammatory drugs (NSAIDs)
- Topical ocular antibiotics
- Topical ocular antihistamines or mast cell stabilizers
- Oral antihistamines
- Topical or nasal vasoconstrictors
- Other investigational products

Within **60 days** prior to screening (Visit 1) and for the duration of the study:

- Topical cyclosporine (Restasis®)
- Any form of topical LE

Within **30 days** prior to the screening visit (Visit 1) alteration to the dose or anticipated alterations to the dose of the following are disallowed:

- Tetracycline compounds (tetracycline, doxycycline, or minocycline)
- Omega-3 or Omega-6 supplements

Within **6 months** prior to the screening visit (Visit 1) alterations to the dose or anticipated alterations to the dose of the following are disallowed:

- Anticholinergics
- Antidepressants
- Isotretinoin
- Oral corticosteroids
- Systemic immunosuppressive agents

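### Does leaving rescue to the investigator while barring all topical eye medication for the whole study undermine the co-primary data?

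*Combined protocol and SAP*

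**What the plan says.** Section 5.2 (Rescue Medication Use) lets the investigator move an inadequately responding subject to other therapy at any time, and "The choice of rescue medication is at the Investigator's discretion". On follow-up it says: "Any subject placed on rescue therapy will discontinue use of the study medication and continue study participation through Visit 6". It adds: "Rescued subjects should not be withdrawn from the study, but rather followed to resolution of signs and symptoms". On status it says: "Rescued subjects will be considered treatment failures, but the need for rescue therapy will not be considered an AE".

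Section 6.2.2 (Medications Not Permitted) lists, from Visit 1 and for the whole study, "Any topical ophthalmic medications including eyelash growth medications, eye drops, gels, or artificial tears". With a 60-day look-back it also bars topical cyclosporine and "Any form of topical LE"; with a 30-day look-back it bars ocular corticosteroids. Exclusion 6 in Section 4.1.2 repeats the bar on topical eye medication. Section 6.2.1 says that medications not excluded in 6.2.2 "may be taken as necessary". Neither 5.2 nor 6.2.2 mentions the other.

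Section 5.3, item 5, gives as one permitted reason for discontinuation: "Subject's failure to comply with protocol requirements or study related procedures".

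Section 9.1.2 defines the primary population as all randomized subjects. The co-primaries are the hyperemia score at Visit 6 and the symptom severity score averaged from Visit 5 to the day before Visit 6. Section 9.4 imputes missing co-primary values under missing at random. The visible Section 9 does not mention rescue.

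**The concern.** The Introduction names artificial tears, topical anti-inflammatory therapy and punctal occlusion as current treatment. Section 6.2.2 bars artificial tears and the topical anti-inflammatory agents it lists, so a likely rescue choice would comply with 5.2 and breach 6.2.2. A site might then score the subject at Day 29 on rescue. It might instead treat the rescue as non-compliance and discontinue under 5.3, with an early score entered on the Visit 6 form (Section 5.1.7). Or it might record no score, which sends the value to imputation. A vehicle subject could even be scored at Visit 6 while using topical loteprednol, the active ingredient.

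Both co-primaries must reach significance (Section 9.3), so a diluted difference on either one would cost the trial its result. The treatment-failure label does not help by itself, because the visible text does not turn it into a value for a mean score.

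**Working it through.** **Step 1: how far the silence of 6.2.2 can be pressed.** Taken word for word, 6.2.2 forbids eye drops and any topical loteprednol throughout the study, and so forbids both study treatments. It also lists oral NSAIDs without the low-dose aspirin exception that exclusion 2b in Section 4.1.2 writes out. The list therefore leaves out at least two exceptions that the protocol plainly intends. The lack of a rescue exception there is weak evidence that none is meant, and the protocol has a separate section devoted to rescue.

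**Step 2: whether the discontinuation route exists.** A site that applies 6.2.2 strictly gives no topical rescue, so there is no breach for 5.3 to act on. A site that gives rescue is acting under 5.2, which tells it not to withdraw the subject. Discontinuing a rescued subject would mean following the first half of 5.2 and ignoring the second. Item 5 of 5.3 is also permissive and concerns the subject's own failure to comply, whereas rescue is the investigator's act. Early-exit scores and imputation apply to any discontinuation and are not created by this mismatch. The realistic contrast is a subject scored at Visit 6 with topical rescue against one scored without it.

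**Step 3: validity of the comparison.** Investigators and assessors are masked (Sections 3.5.2 and 6.5), so a site's rescue habit applies to both arms alike. If the treatments do not differ, rescue and later scores do not differ by arm either. Using every score from all randomized subjects therefore does not inflate type I error. Only the size of a true difference can be affected.

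**Step 4: size.** Section 9.2 states 71 per group and 90% power; its effect size and significance level are redacted. With two-sided 0.05 (the level in Section 9.3), the two-sample t-test implies an effect of 0.548 SD. An assumed 0.55 SD needs 71 per group and has 90.2% power. This agrees with the stated figure but does not reproduce it independently.

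About 150 randomized gives 75 per arm. Power is 1 − F(t₀.₉₇₅,₁₄₈), where F is the noncentral t distribution with 148 degrees of freedom and noncentrality δ√(75/2). At δ = 0.548 this is 91.5% per endpoint.

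Let k be the net excess of rescued subjects on vehicle, and g the score gap in SD for one such subject between two ways of handling rescue. The shift in the drug–vehicle difference is k·g/75. For example, k = 8 and g = 0.5 give 8 × 0.5/75 = 0.053 SD. The documents give neither k nor g; all values are assumptions, with the SD held fixed.

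| k | g (SD) | Shift (SD) | Share of 0.548 | Power if the difference shrinks | Power if it grows |
|---|---|---|---|---|---|
| 2 | 0.25 | 0.007 | 1.2% | 90.9% | 92.1% |
| 2 | 0.5 | 0.013 | 2.4% | 90.2% | 92.7% |
| 2 | 1.0 | 0.027 | 4.9% | 88.7% | 93.8% |
| 8 | 0.25 | 0.027 | 4.9% | 88.7% | 93.8% |
| 8 | 0.5 | 0.053 | 9.7% | 85.3% | 95.5% |
| 8 | 1.0 | 0.107 | 19.5% | 76.5% | 97.8% |

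These are upper bounds, because the formula moves all k subjects from one handling to the other together, while the supposed mechanism is variation between sites. If half of them move, k = 8 and g = 0.5 give 0.5 × 8 × 0.5/75 = 0.027 SD and 88.7% power. A gap of 1.0 SD is nearly twice the planned effect (1.0/0.548 = 1.8). Equal numbers of rescued subjects with equal gaps give no shift.

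**The case for a change.** The strongest case for a change is that no text makes rescue an exception to 6.2.2, and that the agents a site would most naturally reach for are among those barred. A statistical analysis plan can say how scores are used, but it cannot tell a site what it may give or whether giving it is a deviation. The margin over plan is thin: with 75 per arm, 90% power needs 0.533 SD, only 0.015 SD below 0.548. At g = 0.5 a net excess of 75 × 0.015/0.5 = 2.3 subjects uses it up.

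Part of this stands. The sections do not cross-refer, the deviation status of a rescued subject is not spelled out, and the visible Section 9 attaches no score to the failure label. But the clash covers only some choices. Section 5.2 does not require a topical agent, and 6.2.2 does not list punctal plugs; exclusion 15 concerns plugs planned at entry. The margin argument works only once an imbalance and a gap are assumed in one direction, and nothing in the documents supports either. The scoring rule may also be in the separate statistical analysis plan that Section 9 refers to, whose text is not supplied; its absence here does not show that the plan lacks it.

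**Conclusion.** The mismatch in wording is real, but it is a drafting gap and not a rule shown to give a wrong result. Subjects are to be followed to Visit 6 after rescue, all randomized subjects are analysed, and Section 6.2 records start and stop dates for every medication. Analysts therefore have what they need to fix the use of post-rescue scores before unmasking, for both Visit 6 hyperemia and the diary average, and to count rescue by arm.

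No bias direction, power loss or type I error inflation is demonstrated. The illustrative effect on power per endpoint runs from under 1 percentage point (k = 2, g = 0.25) to 15.0 points (k = 8, g = 1.0, difference shrinking: 91.5 − 76.5), on assumed values throughout. The conclusion rests on masking holding, on rescued subjects staying in the study as 5.2 directs, and on 6.2.2 not being meant as an exhaustive bar, since literally it would exclude the study drug. Sections 5.2 and 6.2.2, with exclusion 6, must be reconciled in wording by the sponsor as an editorial matter. This review takes no view on which clinical rule applies, and no change to the statistical plan follows.

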### 6.2. CONCOMITANT MEDICATIONS

All medications that the subject has taken 6 months prior to Visit 1 and through Visit 6 or discontinuation from the study will be recorded in the eCRF and the subject chart. The generic name of the drug, dose, route of administration, duration of treatment (including start and stop dates), frequency, indication, and whether or not the medication was taken due to an AE will be recorded for each medication.

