#### 9.1.2. Analysis of Efficacy

The primary analysis population will be the Intent-to-Treat (ITT) population, defined as all subjects randomized. A subset of efficacy analyses will be examined for the Efficacy Evaluatable (EE) population, the definition of which will be outlined in the Statistical Analysis Plan and finalized prior to unmasking of study data pursuant to clinical data review.

The primary analysis of all ophthalmic efficacy measures will be based on the single study eye for each subject.

The co-primary endpoints are (1) the mean bulbar conjunctival hyperemia score at Visit 6; and (2) the mean [REDACTED] severity score averaged over the days from Visit 5 to the day before Visit 6.

Secondary and exploratory efficacy endpoints will be evaluated as elaborated in [Section 3](#).

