## **9.4. PROCEDURE FOR ACCOUNTING FOR MISSING, UNUSED, OR SPURIOUS DATA**

Any missing, unused, or spurious data will be noted in the final clinical study report. Multiple imputation will be employed to analyze incomplete data sets under the assumption that missing data are, at worst, characterized as missing at random (MAR). The reasons for missing data will be recorded and the impact of these reasons and any treatment group imbalance on the assumption of MAR will be evaluated. Imputation will be carried out only on the co-primary endpoints and time points.

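### Does calling rescued subjects treatment failures leave the co-primary mean-score analysis undefined?

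*Combined protocol and SAP*

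**What the plan says.** Section 5.2 lets a subject who is not responding adequately be rescued; such subjects "may be rescued and placed on alternate therapy at the Investigator's discretion at any time". It continues: "Any subject placed on rescue therapy will discontinue use of the study medication and continue study participation through Visit 6". It then classifies them: "Rescued subjects will be considered treatment failures, but the need for rescue therapy will not be considered an AE".

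Section 9.1.2 sets the analysis: "The primary analysis population will be the Intent-to-Treat (ITT) population, defined as all subjects randomized". "The co-primary endpoints are (1) the mean bulbar conjunctival hyperemia score at Visit 6", and the second is the diary severity score averaged over roughly the last week, from Visit 5 up to the eve of Visit 6. The visible rows of Sections 3.1 to 3.3 and Table 1 contain only mean values and mean changes from baseline, with no responder or failure endpoint.

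Section 9.4 covers gaps in the data: "Multiple imputation will be employed to analyze incomplete data sets", on a missing-at-random assumption and for the co-primary endpoints only. It does not mention rescue.

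Section 6.2.2 lists what may not be taken from Visit 1 onward, including "Any topical ophthalmic medications including eyelash growth medications, eye drops, gels, or artificial tears". It makes no exception for rescue. Section 6.2 requires each medication's "duration of treatment (including start and stop dates") to be recorded.

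**The concern.** The failure label in Section 5.2 has no visible consequence. A subject rescued before Visit 5 contributes both co-primary values entirely while on another treatment. Those values are observed, so multiple imputation does not touch them. A subject declared a failure could therefore enter the assigned arm's mean with a good score.

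If rescue works and is commoner on vehicle, the vehicle mean improves for reasons unrelated to vehicle and both differences shrink. If rescue is sufficiently commoner on drug, the differences could grow instead. Both co-primaries must reach significance (Section 9.3), so a loss on either one fails the trial. A rule left unwritten also raises the worry that it could be chosen after unmasking.

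There is a second, textual tension. Section 5.2 leaves the choice of rescue medication to the investigator, while Section 6.2.2 bars topical ophthalmic medications for the whole study.

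**Working it through.** **Inputs from the documents.** 71 per group, 90% power, two-group t-test, two-sided (Section 9.2); 0.05 for each co-primary (Section 9.3); about 150 randomized roughly 1:1, so about 75 per arm (Section 3.5). The effect size and significance level in Section 9.2 are redacted.

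**The plan's own figure.** It cannot be reproduced directly, so the effect size is back-solved. With noncentral-t power at n = 71 and two-sided 0.05, 90% power requires d = 0.548 SD. As a check, d = 0.55 gives n = 71 with 90.2% power. The stated size is consistent with an effect near 0.55 SD. At 75 per arm, d = 0.548 gives 91.5%.

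**Assumed, not in the documents.** Vehicle and drug rescue rates rv and ra, and the benefit g of rescue in SD. SD is held at 1. Power is per endpoint.

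*Model A: rescued drug subjects would otherwise have had the average drug effect.* Analysed effect = d(1 − ra) + g·ra − g·rv.

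With g = d this reduces to d(1 − rv), whatever ra is:

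| rv | Effect (SD) | Power, 71 per arm | Power, 75 per arm |
|---|---|---|---|
| 0 | 0.548 | 90% | 92% |
| 5% | 0.548 × 0.95 = 0.520 | 87% | 89% |
| 10% | 0.548 × 0.90 = 0.493 | 83% | 85% |
| 20% | 0.548 × 0.80 = 0.438 | 74% | 76% |

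If the redacted level were 0.025 or 0.10, with d re-solved to 0.597 or 0.494, the 10% case at 71 per arm would be 82% or 84%.

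With stronger rescue, g = 1.0, at 71 per arm:
- rv = 10%, ra = 3%: 0.548 × 0.97 + 0.03 − 0.10 = 0.461 SD, power 78%.
- rv = 5%, ra = 20%: 0.548 × 0.80 + 0.20 − 0.05 = 0.588 SD, power 94%.
- Inflation requires ra/rv > g/(g − d) = 1/0.452 = 2.2.

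*Model B: rescued drug subjects are non-responders.* Analysed effect = d + g(ra − rv). With g = 0.548, rv = 10%, ra = 3%: 0.548 − 0.548 × 0.07 = 0.509 SD, power 85%. Equal rates give no shift; any excess on drug inflates.

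*No drug effect.* Setting d = 0 in either model leaves g(ra − rv), which is zero when rescue is equally common in the two arms.

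**The alternative, a failure score.** With d = 0.55 and each rescued subject scored 0.5 to 1.0 SD worse than the vehicle mean (spread of the mixture included), power at 71 per arm is:

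| Rescue, vehicle / drug | As observed (g = d) | Failure score |
|---|---|---|
| 5% / 2% | 86.9% | 90.2–90.8% |
| 10% / 5% | 82.9% | 88.9–89.7% |
| 20% / 5% | 73.0% | 93.3–96.2% |

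These columns answer different questions: the arms as treated, rescue included, against an outcome in which rescue itself counts as a bad result. A higher power does not make the second the correct one.

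**What a replacement rule costs.** One candidate takes the worse of the baseline and the last pre-rescue score. For two normal values with equal means, unit SD and correlation ρ, the expected worse value exceeds the mean by √((1 − ρ)/π). At assumed ρ = 0.5 that is √(0.5/3.142) = 0.40 SD; at ρ = 0.7, √(0.3/3.142) = 0.31 SD. Each rescued subject is pushed that far in the bad direction by construction, which favours the arm with less rescue. Hyperemia is graded only at Visits 1, 2, 4 and 6 (Appendix 4), so for a rescue before Visit 4 the rule normally just carries the Visit 2 value forward.

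**The case for a change.** The strongest case for a change is that the protocol states a classification and then never uses it. Scores on rescue are not missing, so Section 9.4 cannot be stretched to cover them, and the handling rule alone moves power from 73% to above 93% in the most extreme row above. The remedy would be cheap: wording and a rescue-date flag built from medication dates already collected.

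Part of that stands. No visible sentence settles the handling, the arithmetic is right, and a sentence would have been welcome. Three parts do not carry through.

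First, silence here is weak evidence of omission. Section 9 is an outline: it does not name the primary model, its covariates or the use of the stratification factors either. Sections 9.1.2 and 9.5 point to a separate analysis plan as the governing text. The one item expressly deferred to it, the Efficacy Evaluable definition, is to be fixed before unmasking, and nothing suggests that rescue handling would be left until later.

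Second, the failure label need not feed a mean score to have a use. It can serve disposition and descriptive reporting, and Section 5.2 does not tie it to the co-primaries.

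Third, the extreme row rests on 20% vehicle rescue within 28 days, which nothing in the documents supports. The inflation example needs four times as much rescue on drug and a rescue benefit nearly twice the back-solved drug effect. Model B inflates more readily, but it still needs more rescue on drug than on vehicle.

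The tension between Sections 5.2 and 6.2.2 is genuine on the page. The two passages must be reconciled, for which a cross-reference is enough. It alters no analysis result.

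**Conclusion.** The concern does not call for a change. This is a detail the protocol leaves unwritten and that analysts would fill sensibly, combined with a fair trade-off between two legitimate strategies. All-randomized analysis, with rescued subjects kept and measured to Visit 6, leads to using scores as observed in the assigned arm. That reading is coherent and contradicts no stated figure. Replacing those scores would swap a mostly power-reducing effect for a constructed penalty that can favour the drug when vehicle rescue is commoner.

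Under the assumed case of rescue as effective as the drug, the cost of the default is about 3 percentage points of per-endpoint power at 5% vehicle rescue and about 7 at 10%. It is about 16 points at 20%, whether 71 or 75 per arm are analysed. These sizes rest on a back-solved 0.548 SD, a two-sided 0.05 level and rescue rates that the documents do not give. Knowing the actual rescue counts by arm, or the text of the separate analysis plan, would settle how much of this is more than theoretical.
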